### 11. TelephoneEvent

- The table will keep a list of telephone events that can be applied to a donor.
  - oFirst Call
  - oFollow-up Call
  - oReminder

oReturned Call

TelephoneEvent	
PK	TelephoneEventID
	Event

Field	Description	Field Type
TelephoneEventID	Unique number generated internally by system.	INTEGER
Event	The telephonic event that can be applied to a donor	VARCHAR(20)

**12. TelephoneHistory**

- The table will keep a list of telephone correspondence between SANBS and the donor. If the donor phones SANBS that event can also be recorded on the donor's record.

TelephoneHistory	
PK	TelephoneHistoryID
FK1	TelephoneEventID
FK2	DonorID
	TelephoneNumber
	Description
	UserID
	TelephoneDate
	TelephoneDateTS

Field	Description	Field Type
TelephonHistoryID	Unique number generated internally by system.	INTEGER
TelephoneEventID	The telephonic event that can be applied to a donor	VARCHAR(20)
DonorID	The donor record to which the event is linked (Foreign key with Donor table)	INTEGER
TelephoneNumber	The telephone number that was dialled.	VARCHAR(20)
Description	A description of what the call was about.	VARCHAR(200)
UserID	The user who added the telephone event to the donor record.	INTEGER
TelephoneDate	The date on which the call was made or received	DATE
TelephoneDateTS	The date that the above value has been added to the system. Added by system.	DATE

### 13. DonorHistory

- The table will keep a history of changes made to the donor. The table will have a field for the old value as well as a field for the new changed value.

DonorHistory	
PK	DonorHistoryID
FK1	DonorID Field OldValue NewValue DateTS
FK2	UserID

Field	Description	Field Type
DonorHistoryID	Unique number generated internally by system.	INTEGER
DonorID	The donor record to which the event is linked (Foreign key with Donor table)	INTEGER
Field	The field that has changed e.g. donor name , number etc.	VARCHAR(30)
OldValue	The original value of the field that has changed.	VARCHAR(30)
NewValue	The new value of the field that has changed.	VARCHAR(30)
DateTS	The date that the change was made to the system. Added by system.	DATE
UserID	The user who has made the change. (Foreign key with User table)	INTEGER

[figure not shown]
### 14. Appointment Outcome

- We need a table that can keep track of the outcome of each appointment whether successful or not for example,
  - o donor may commit to come, but does not pitch up or
  - o donor refuses to come
  - o counseled in person
  - o counseled and tested

### 15. Case Outcome

- We need a table that can keep track of the outcome of each case, i.e. when it is “closed”; what was the final outcome of the case, for example:
  - o Never located

- Firm refusal
- Passive refusal
- Successful counseling

**C.Timeline:**

	Planned Date	Actual Date
Initial Investigation:		
Execution:		
Testing:		
Training:		
Planned Go Live:		

**D.Costs:**

Resources	Man Days	Estimated Cost	Actual Man Days	Actual Cost
Business Analyst:				
Developer:				
Consultant:				
Total IT Cost				
User:				
Training:				
Other:				
Total Cost				

**E.Deliverables:**

A database that will contain records for the counselling of marker positive donors. The database will enable SANBS to develop reporting functionality that can be used for statistical purposes.

**F.Risk Analysis:**

To be defined.

**G.Test Plan:**

The test plan will be defined in the next draft after the graphical user interface has been scoped.

#### **H.Implementation Issues:**

Too early to define as database structure is only being developed.

#### **I.Implementation Plan (Including Training and DRP):**

To be defined.

#### **J.Configuration Changes:**

A database with the following tables:

- Donor
- DonorStatus
- Virology
- Province
- Zone
- User
- JobTitle
- Counsellor
- Letter
- DonorLetter
- TelephoneEvent
- TelephoneHistory
- DonorHistory

## **Appendix 7 HIV and HBV Risk Factor Questionnaire**

**Incident HIV/Hepatitis B Virus infections in South African blood donors:  
Behavioural risk factors, genotypes and biological characterization of early infection**

**Blood Donor Risk Factor Study Questionnaire (English)**

**SECTION A – GENERAL STUDY DATA**

**This section is to be completed by the research assistant or other research staff.**

A1. Participant ID (*Internal study number to be assigned by Study Management System*)

\_\_\_\_\_

A2. Participant donor number (*Number that will link with donor’s Meditech info*)

\_\_\_\_\_

- 97      Don't Know
- 98      Refuse to Answer
- 99      Not Applicable

A3. Blood collection site. (*Blood collection site neumonic (clinic site code). The neumonic can be mapped back to Branch, Zone or Province – this will have to be coded during analysis phase*)

\_\_\_\_\_

**UID = Concatenated(A3, A1)**

A4. Month of interview (Choose one)

- 01 January
- 02 February
- 03 March
- 04 April
- 05 May
- 06 June
- 07 July
- 08 August
- 09 September
- 10 October
- 11 November
- 12 December

A5. Year of interview (please enter four numbers)

\_\_\_ \_\_\_ \_\_\_ \_\_\_      YYYY

**YEAR2 = A5 - 1**

A6. Research Staff Initials: \_\_\_ \_\_\_ \_\_\_ \_\_\_

A7. Type of Participant (Choose one)

- 1 Study group 1 (won't appear on screen: HIV case)
- 2 Study group 2 (won't appear on screen: HBV case)
- 3 Study group 3 (won't appear on screen: Control)

**INSTRUCTION to RESEARCH STAFF: If study participant is not already sitting at the computer, at this time please make sure the study participant is sitting at the computer and has put the headphones on.**

**SECTION B - DEMOGRAPHIC DATA**

**APPEARS ON SCREEN and HEARD if ACASI: This study has been approved by Ethical Committees in South Africa and the USA. This study also has been approved by the Office of Management and Budget; OMB XXXX, OMB approval expires XX, XXXX, 201X.**

**APPEARS ON SCREEN and HEARD if ACASI: We are asking you to respond as truthfully as you can. Please keep in mind that the questions are part of a scientific study, and the researchers will make every effort to keep your responses confidential. However, there is a small chance that your responses may not be kept confidential, but your name is not collected on the questionnaire and your responses cannot be easily traced back to you. Please answer these questions to the best of your knowledge and as truthfully as you can. You may skip any questions that you are not comfortable answering.**

**In this section of the questionnaire the research assistant will show you how to use the computer to answer the interview questions. After completing this section, with help from the research assistant, you will be left to complete the interview in private. If you have any questions at any time or are unsure of what to do, please ask for help.**

B1. What is your gender? (Choose one)

- |    |                  |
|----|------------------|
| 1  | Male             |
| 2  | Female           |
| 3  | Transgender      |
| 97 | Don't Know       |
| 98 | Refuse to Answer |

B2. What is your birth year?

— — — —

- |      |                  |
|------|------------------|
| 9997 | Don't Know       |
| 9998 | Refuse to Answer |

B3. What is your birth month? (Choose one)

January

February

March

April

May

June

July

August

September

October

November

December

Don't Know

Refuse to Answer

B4. What is your birth day?

97 Don't Know

98 Refuse to Answer

B5a. What is your country of birth? (Choose one)

- 1 South Africa
- 2 Zimbabwe
- 3 Malawi
- 4 Mozambique
- 5 Swaziland
- 6 Botswana
- 7 Lesotho
- 8 Namibia
- 9 Nigeria
- 10 Other
- 97 Don't Know
- 98 Refuse to Answer

***If B5a is not equal to 10, then skip to instruction before B6.***

B5b. Please tell us your country of birth.

---

***READ and HEARD: From now on, you will be left alone. It means that you will have total privacy to answer all these questions. Please, if you have any questions call the research assistant for help.***

B6. What is your race / ethnic origin? (Choose one)

- 1 Black
- 2 White
- 3 Coloured
- 4 Asian
- 6 Other
- 97 Don't Know
- 98 Refuse to Answer

B7. What is the primary language that you speak at home? (Choose one)

- 1      isiZulu
- 2      isi Xhosa
- 3      Afrikaans
- 4      Sepedi
- 5      Setswana
- 6      English
- 7      Sesotho
- 8      Xitsonga
- 9      siSwati
- 10     Tshivenda
- 11     isiNdebele
- 12     Other
- 98     Refuse to Answer

B8. What is your current marital status? (Choose one)

- 1 Single, never married.
- 2 Living with partner, but not married.
- 3 Married to one partner (including traditional marriage).
- 4 Married to more than one partner (including traditional marriages).
- 5 Separated/divorced.
- 6 Widowed.
- 97 Don't Know
- 98 Refuse to Answer

B9a. Is your primary sexual partner?

- 1 Male
- 2 Female
- 3 Transgender
- 4 Do not have a primary sexual partner **Skip to B10.**
- 97 Don't Know
- 98 Refuse to Answer

B9b. Are you currently living with your primary sexual partner? (**ONLY ask if B8 = 2, 3, or 4**)

- 0 No
- 1 Yes
- 98 Refuse to Answer

B10. What is the highest level of education you have completed? (Choose one)

- 0 Never been to school
- 1 Up to Grade 7 / Standard 5
- 2 Up to Grade 10 / Standard 8
- 3 Up to Grade 12 / Standard 10
- 4 Incomplete further degree or qualification (some college or technical school)
- 5 College or technical qualification
- 6 University or professional degree
- 97 Don't Know
- 98 Refuse to Answer

B11. What is your religion or affiliation? (Choose one)

- 1. Christianity
- 2. Islam
- 3. Hinduism
- 4. Judaism
- 5. African traditional beliefs
- 6. Other faiths
- 7. No religion
- 97 Don't Know
- 98 Refuse to Answer

B12a. Do you have medical aid?

0 No

1 Yes

98 Refuse to Answer

B12b. Do you self-fund access (pay out of pocket) to private hospital?

0 No

1 Yes

98 Refuse to Answer

B13c. Are you currently working?

1 Yes, self-employed

2 Yes, employed full or part-time

3 No, unemployed **SKIP to Section C**

97 Don't know

98 Refuse to Answer

B13b. What type of work are you doing?

1 Mining

2 Transport/cargo delivery

3 Military/police

4 Medical/healthcare

- 5 Business/sales/retail
- 6 Farming
- 7 Teacher/ education/ student
- 8 General labour (domestic worker, gardener, janitorial)
- 9 Civil service (examples including working in government office, post office)
- 10 Other
- 97 Don't Know
- 98 Refuse to Answer

B13c. *If B13b=10 Else SKIP* What is your occupation?

-----

B14a. In the last 6 months have you spent a total of four weeks or more away from your primary residence (home)?

- 0 No
- 1 Yes
- 97 Don't Know
- 98 Refuse to Answer

*If B14a equals 0, then skip to B15a.*

B14b. What was the primary purpose for being away during this period?

- 1 Work

- 2 Looking for work
- 3 Holiday
- 4 Other, specify: \_\_\_\_\_

B15a. How many nights did you sleep at your primary residence (home) in the past six months?

- 1 Every night
- 2 Most nights
- 3 About half of the nights
- 4 Fewer than half of the nights

B15b. How long has your pattern of sleeping at your primary residence (home) been the same as it has been in the past six months?

- 1 It has been like this only in the past 6 months
- 2 It has been like this for only the past year
- 3 For one to five years
- 4 For five years or more

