#### **4. Objectives**

1a: To identify the demographic and behavioural risk factors associated with incident HIV infection (based on “NAT yield” or LAg Avidity testing) among blood donors in South Africa.

Hypotheses: 1) The risk factors for incident HIV in blood donors in South Africa will include a recent change in sexual partner, older male/younger female sexual partnership, a greater number of recent sexual partners, unprotected receptive anal intercourse, and lower socioeconomic status.

1b: To identify the demographic and behavioural risk factors associated with incident HBV infection among blood donors in South Africa identified as “NAT-yields” or concordant serology and NAT positive and anti-HBc negative.

Hypotheses: 1) The risk factors for incident HBV in blood donors in South Africa will include greater number of recent sexual partners, recent scarification/tattoo/body markings, and history of personal contact with an HBV-infected person.

2a: To determine HIV subtype and drug resistance profiles among HIV positive donors with recently acquired infection based on year of donation and site of collection, and examine findings with donor demographics and risk behaviors derived in Objective 1.

Hypotheses: 1) The proportion of donors identified with incident HIV infection containing drug resistance mutations will be positively related to the proportion of HIV-positive individuals receiving anti-retroviral therapy at a population-level in South Africa

2b: To determine HBV genotype profiles among HBV positive donors with recently acquired infection based on year of donation and site of collection, and correlate findings with donor demographics and risk behaviors derived in Objective 1

Hypotheses: 1) Incident HBV infections will show differences in genotypes with genotype E increasing when compared to public health data on prevalent infections.

3: To prospectively characterize the virology, immunology and natural history of incident HIV infection among a cohort of recently infected blood donors and a small group of elite controllers in South Africa.

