#### **4.2.2. Control Recruitment and Enrollment**

SANBS collection sites are administratively organized into zones, branches, and clinic sites. Clinics can be fixed or mobile collection sites. To meet the study criterion of matching by geographic area, controls will be selected from clinics within the branches from where persons with recently acquired HIV infection have been identified. To minimize selection bias, clinics within each branch will be randomly selected by the study statisticians. On recruitment days at the randomly selected clinics, individuals that are demographically matched potential controls (age within 5 years, and by population group) will be randomly selected using systematic sampling and approached for enrollment into the study as a “potential control”. Our study documents and consents indicate the “potential control” designation, and explain the meaning of this term. Following successful donation the potential controls will be invited to complete the ACASI study questionnaire. After each donation has been tested and if the donor tests negative for all infections, the person will be reclassified in the database as a control.

The characteristics of individuals with recent HIV and HBV infection (per NAT-only over a 5 year period) are substantially similar for the three matching variables for the study cases and controls (see Table 3). As such, we intend to use a subset of the controls matched for the HIV portion of the study to serve as controls for the HBV objective.

Table 3. Demographic characteristics of HIV NAT only and HBV NAT only positive donors at SANBS for the years 2006 – 2010.

Demographic Characteristic		HIV (n=300)		HBV (n=248)	
		Number	Percent	Number	Percent
Gender	Female	174	58.0	108	43.5
	Male	126	42.0	139	56.0
	Missing	0	0.0	1	0.4
Population Group	Asian	6	2.0	12	4.8
	Black	251	83.7	161	64.9
	Coloured	12	4.0	10	4.0
	White	29	9.7	63	25.4
	Missing	2	0.7	0	0.0
Age Group	16-19 years	49	16.3	43	17.3
	20-25	90	30.0	69	27.8
	26-30	59	19.7	43	17.3
	31-40	60	20.0	52	21.0
	41-50	32	10.7	24	9.7
	51-60	10	3.3	10	4.0
	61-70	0	0.0	7	2.8
SANBS Region	Eastern Cape	24	8.0	18	7.3
	Egoli (Johannesburg)	43	14.3	34	13.7
	Free State/Northern Cape	29	9.7	28	11.3
	KwaZulu Natal (Durban)	83	27.7	60	24.2
	Mpumalanga	35	11.7	30	12.1
	Northern (Pretoria)	52	17.3	31	12.5
	Vaal	34	11.3	47	19.0

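### Appendix 7's employment item codes non-working students, homemakers and retirees as unemployed and skips non-working students past the only student code, blurring one of the few socioeconomic proxies for hypothesis 1a

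*Protocol*

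**What the plan says.** Appendix 7, Section B, asks about work in the item printed as "B13c. Are you currently working" (the label B13c appears again on the later occupation item). The substantive answers are "Yes, self-employed", "Yes, employed full or part-time" and "No, unemployed"; Don't know and Refuse are also offered. The third answer carries a routing instruction: "3 No, unemployed SKIP to Section C". The next item, B13b, asks the type of work, and its code 7 is "Teacher/ education/ student". No other item in Section B asks about current study.

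Section 4 (Objectives) lists among the expected risk factors for incident HIV "unprotected receptive anal intercourse, and lower socioeconomic status", and Section 4.9 repeats socioeconomic status as a predictor for objective 1a. Neither section says which questionnaire items measure it.

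**The concern.** The instrument lists student as an answer but places it behind a question about working. A full-time student without a job has to answer that question with the unemployed code and is then sent out of the section. Homemakers and retirees get the same code. The stored value therefore mixes people seeking work with people outside the labour force, and no later analysis can fully separate them, because the distinction is not collected.

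What is at stake is the measurement of a pre-stated predictor. Appendix 7 has no income item. The usable proxies are education (B10), medical aid (B12a), self-paid private hospital access (B12b) and employment or occupation (B13). Donors with incident infection are young, and controls are matched to within 5 years of age, so students may be numerous in both groups. Age matching does not tell a student from a job-seeker of the same age.

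**Working it through.** **Routing, code by code**
- Codes 1 and 2 (working) go on to B13b, so a working student can reach code 7.
- Code 3 (not working) goes to Section C. B13b is not seen. B14a to B15b (time away from home, nights at home) are also lost, although B14b offers a job search as a reason for absence.
- Codes 97 and 98 have no printed skip and fall through to B13b.

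The student code is thus closed to non-working students who choose code 3, and open to other students. The partner matrix repeats the pattern: code 3 of F10b skips F10c, whose code 6 again pools students with teachers.

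**How young the donors are** (Table 3, "Demographic characteristics of HIV NAT only and HBV NAT only positive donors at SANBS for the years 2006" to 2010)
- HIV, ages 16–25: (49 + 90)/300 = 139/300 = 46.3%.
- HBV, ages 16–25: (43 + 69)/248 = 112/248 = 45.2%.

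These are age shares, not student shares. They include 16- and 17-year-olds, whom Section 4.1.2 excludes.

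**Possible dilution.** The protocol states no figure to reproduce, and all inputs here are assumptions. Let s, j and e be the shares of controls who are non-working students, job-seekers and employed, and let ORs and ORj be the odds ratios of the first two against the employed. The coded odds ratio is

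[(s·ORs + j·ORj)/e] / [(s + j)/e] = (s·ORs + j·ORj)/(s + j),

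a weighted average of the two. With ORj = 2.0:

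| s | j | ORs | Coded OR |
|---|---|---|---|
| 0.10 | 0.20 | 1.0 | 0.50/0.30 = 1.67 |
| 0.20 | 0.20 | 1.0 | 0.60/0.40 = 1.50 |
| 0.20 | 0.10 | 0.7 | 0.34/0.30 = 1.13 |
| 0.28 | 0.10 | 0.7 | 0.396/0.38 = 1.04 |
| 0.05 | 0.20 | 1.0 | 0.45/0.25 = 1.80 |
| 0.10 | 0.20 | 1.5 | 0.55/0.30 = 1.83 |
| any | any | 2.0 | 2.00 (no bias) |

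**Second illustration, on power.** Take job-seekers as 20% of controls and 30% of cases. These proportions are borrowed from the second row of Table 8, where they describe multiple partners, not unemployment. Let a fraction c of all other donors be students coded unemployed, equal in both groups. The coded proportions are 0.20 + 0.80c in controls and 0.30 + 0.70c in cases.
- c = 0: 0.20 and 0.30, OR 1.71, power 0.94.
- c = 0.10: 0.28 and 0.37, OR 1.51, power 0.83.
- c = 0.20: 0.36 and 0.44, OR 1.40, power 0.69.

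Power is for a simple two-proportion comparison of 300 cases with 900 controls, ignoring clustering by clinic.

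**The case against.** The strongest reply is that the harm to hypothesis 1a is inferred. The protocol names no item or index for socioeconomic status and specifies no unemployment odds ratio; building the measure is ordinary content for an analysis plan, which is not at hand. Three other proxies are unaffected. Birth year, the incomplete-further-education code in B10 and medical aid together partly distinguish a student from a job-seeker. Appendix 7 is also visibly a draft, with an OMB number still to be filled in and a pilot planned in Section 4.11.

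Much of this stands as a limit on size, but it does not remove the defect. The B10 code also catches people who dropped out, and a first-year student may report Grade 12, so reconstruction is partial. An analysis plan cannot recover an answer that was never offered. The draft status is a reason to correct the item now.

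Three stronger readings are tempting and not supported:
- A reader might infer that no student can reach the student code. Working students and those answering 97 or 98 can.
- A reader might infer that employment is the study's main socioeconomic measure. The protocol does not say so; it is one of a few proxies.
- A reader might infer that a real association will be masked. That depends on students having lower risk than job-seekers and on a student share that the protocol does not give.

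**Conclusion.** The defect is confirmed from the text: the item misclassifies people outside the labour force as unemployed, and routes the non-working students among them away from the only student code. It also drops B14a to B15b for every non-worker.

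The effect on the unemployment odds ratio cannot be sized from the protocol. If non-working students are 10–28% of controls, job-seekers 10–20% with an odds ratio of 2.0, and students have an odds ratio of 0.7–1.0, the coded odds ratio lies between 1.04 and 1.67. With few students, or with student risk nearer that of job-seekers, it is about 1.8; with equal risk there is no bias. The low end needs several unfavourable assumptions at once. Homemakers and retirees are left out of these sums. The point is worth correcting because the distinction is irrecoverable once data are collected and the change is small. It does not show that hypothesis 1a would fail.

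**What to change.** In Appendix 7, Section B:
1. Split code 3 of the work item into three: not working and looking for work; not working and a student; not working for another reason (homemaker, retired, unable to work).
2. Route all three past B13b and the occupation item to B14a instead of Section C. Without this routing the new codes would either fall through to a question about type of work or still lose B14a to B15b.
3. Give students their own code in B13b, apart from teachers and education, so that working students can also be identified.
4. Relabel the work item so that B13c is used once.

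Make the matching change in F10b and F10c of the partner matrix. In the analysis, keep students as a separate category of the employment variable.

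The cost is a few response options and, for non-workers, the four short items B14a to B15b. Section 4.6 requires OMB approval of the instruments and allows up to nine months for it, so the change is cheap only if made before that submission and before the ACASI is programmed.

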**SECTION H - ALCOHOL AND DRUG USE**

**READ and HEARD:** Now we are going to ask you some general questions regarding alcohol and drug use. Some types of alcohol or drug use can be related to the risk of becoming infected with HIV or HBV. Once again, the following questions are intended to help us determine how to improve the safety of donated blood. We are asking you to respond as truthfully as you can. The answers are confidential. Your individual responses will not be known by SANBS. Your answers will be reported together with all other people who complete the questionnaire.

H1. How often do you drink beer, wine, liquor, or mixed drinks? (Choose one)

- |    |                             |                   |
|----|-----------------------------|-------------------|
| 0  | Never                       | Skip to H4 |
| 1  | 1-3 times per month or less |                   |
| 2  | 1-2 times per week          |                   |
| 3  | 3-6 times per week          |                   |
| 4  | Everyday                    |                   |
| 97 | Don't Know                  |                   |
| 98 | Refuse to Answer            |                   |

H2. On average how many drinks do you have each time you drink? (When answering, one drink is a glass of wine or a beer or a mixed drink.)

Number of drinks         

997 Don't Know

H3a. Have you ever used dagga, marijuana, or hashish? (Choose one)

- |    |                  |                    |
|----|------------------|--------------------|
| 0  | No               | Skip to H4a |
| 1  | Yes              |                    |
| 97 | Don't Know       |                    |
| 98 | Refuse to Answer |                    |

H3b. When was the first year you used dagga, marijuana or hashish?

— — — — YYYY

2097 Don't Know (Year)

2098 Refuse to Answer (Year)

***If H3b is less than B2 then READ and HEARD: "The year that you entered for first year of dagga, marijuana, or hashish drug use is smaller than the year you were born. Please correct the year of your first dagga, marijuana, or hashish drug use." (Returns to H3b)***

H3c. When was the last year you used dagga, marijuana or hashish?

— — — — YYYY

2097 Don't Know (Year)

2098 Refuse to Answer (Year)

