***If H3c is less than H3b then READ and HEARD: "The year that you entered for last year of dagga, marijuana, or hashish drug use is smaller than the year of your first reported dagga, marijuana, or hashish drug use. Please correct the last year of your dagga, marijuana, or hashish drug use." (Returns to H3c)***

H4a. Have you ever used whoonga which is also known as nyaope? (Choose one)

0 No **Skip to H5a**

1 Yes

97 Don't Know

98 Refuse to Answer

H4b. When was the first year you used whoonga or nyaope?

— — — — YYYY

2097 Don't Know (Year)

2098 Refuse to Answer (Year)

**If H4b is less than B2 then READ and HEARD: "The year that you entered for first year of whoonga or nyaope drug use is smaller than the year you were born. Please correct the year of your first whoonga or nyaope drug use." (Returns to H4b)**

H4c. When was the last year you used whoonga or nyaope?

— — — —      YYYY

2097      Don't Know (Year)

2098      Refuse to Answer (Year)

**If H4c is less than H4b then READ and HEARD: "The year that you entered for last year whoonga or nyaope drug use is smaller than the year of your first reported whoonga or nyaope drug use. Please correct the last year of your whoonga or nyaope drug use." (Returns to H4c)**

H5a. Have you ever used any non-injected drugs (drugs that are smoked, snorted or taken orally), examples include tik, mandrax, "glue", cocaine (crack), methamphetamines (crystal), ecstasy ("E") and LSD? (Choose one)

0      No      **Skip to H7**

1      Yes

97      Don't Know

98      Refuse to Answer

H5b. When was the first year you used non-injected drugs?

— — — —      YYYY

2097      Don't Know (Year)

2098      Refuse to Answer (Year)

**If H5b is less than B2 then READ and HEARD: "The year that you entered for first year of non-injected drug use is smaller than the year you were born. Please correct the year of your first non-injected drug use." (Returns to H5b)**

H5c. When was the last year you used non-injected drugs?

— — — —      YYYY

2097      Don't Know (Year)

2098      Refuse to Answer (Year)

***If H5c is less than H5b then READ and HEARD: "The year that you entered for last year non-injected drug use is smaller than the year of your first reported non-injected drug use. Please correct the last year of your non-injected drug use." (Returns to H5c)***

H6. If you have smoked or snorted drugs, did you share pipes or straws with another person? (Choose one)

1      Always

2      Sometimes

3      Never

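### Three routing lines in the Appendix 7 questionnaire are wrong as printed and would lose mobility, dagga and vaginal-practice data for identifiable groups of respondents

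*Protocol*

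**What the plan says.** Appendix 7 of the protocol prints the risk factor questionnaire with its skip rules. Three of them matter here.

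- **Section B, employment item** (the one before B13b). Unemployed respondents are told "SKIP to Section C". Before Section C come the occupation items, then B14a (four weeks or more away from home in six months), B14b (purpose of the absence, with "Looking for work" among the options), B15a ("How many nights did you sleep at your primary residence (home) in the past six months") and B15b (how long that pattern has lasted).
- **Section H, item H1** ("How often do you drink beer, wine, liquor, or mixed drinks"). The Never answer goes to H4. Between the two lie H2 (drinks per occasion) and H3a to H3c, which open with "Have you ever used dagga, marijuana, or hashish". The landing item, printed as H4a, is "Have you ever used whoonga which is also known as nyaope".
- **Section J, item J16a** (vaginal drying, cleaning or tightening). The condition is given in words as female and in code as B2=2. In Section B, item B2 is "What is your birth year"; gender is B1, with code 2 for female.

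Section 4.9 says that predictors beyond the named ones will be examined in Objectives 1a and 1b, and that missing data will be handled by weighting and/or multiple imputation.

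**The concern.** A skip rule should remove only questions that cannot apply. The first two rules remove questions that do apply, and the third tests the wrong variable. Being out of work gives no reason to omit nights spent at home, and abstaining from alcohol gives no reason to omit cannabis.

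The resulting gaps are structural: whether the item is missing is fixed by the answer to another item. Weighting and imputation need some respondents in the affected group who did answer, and under the printed routing there are none. Imputed mobility values for the unemployed would be extrapolated from everyone else, and imputed dagga values for non-drinkers would be extrapolated from drinkers. For J16a and J16b there might be nothing to extrapolate from. A further risk is that an analyst reads a skipped item as a negative answer.

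**Working it through.** **Step 1. Follow the printed order and skip targets.**

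| Trigger | Target | Items passed over | Rightly omitted | Wrongly omitted |
|---|---|---|---|---|
| Employment item = unemployed | Section C | B13b, B13c (occupation), B14a, B14b, B15a, B15b | B13b, B13c | B14a, B14b, B15a, B15b |
| H1 = Never | H4 (printed as H4a) | H2, H3a, H3b, H3c | H2 | H3a, H3b, H3c |
| J16a shown only if B2=2 | – | J16a, J16b | – | J16a, J16b for every woman |

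**Step 2. Check against the rest of the instrument.** Routing in Sections E, F and G uses B1 for gender. The consistency checks in Sections H and I compare first-use and first-transfusion years with B2, so B2 is birth year throughout. No birth year equals 2, so the coded condition is never true. In Section H, a non-drinker is still asked about whoonga (H4a), non-injected drugs (H5a) and injected drugs (H7a); among the drug-use questions, only the dagga items are lost. H3a's own skip goes to H4a, so the H4 target at H1 looks like an outdated item number.

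**Step 3. Size of the mobility and dagga gaps.** The protocol gives no share of unemployed donors or non-drinkers. Let *u* be the assumed share routed past an item, equal in all groups. Planned numbers are 300 HIV cases, 150 HBV cases and 900 controls, 1,350 in total.

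- *u* = 10%: 30 + 15 + 90 = 135 not asked; the HIV comparison becomes 270:810.
- *u* = 40%: 120 + 60 + 360 = 540 not asked; the HIV comparison becomes 180:540.

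**Step 4. Power among those asked (illustration only).** Take the first row of Table 8, exposure 0.25 in cases and 0.15 in controls, three controls per case, two-sided 5%, no clustering. With *n* cases, pooled proportion 0.175:

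- SE under the null = √[0.175 × 0.825 × (1/*n* + 1/3*n*)]
- SE under the alternative = √[0.25 × 0.75/*n* + 0.15 × 0.85/3*n*]
- Power = Φ[(0.10 − 1.96 × SE null) / SE alternative]

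For *n* = 300: Φ[(0.10 − 1.96 × 0.0253)/0.0277] = 0.97. For *n* = 270: 0.95. For *n* = 180: 0.84. These are not comparable with the protocol's clustered simulation. They show only that the main loss is an unobserved group rather than power.

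**Step 5. Size of the J16 gap.** Table 3 has 58.0% women among HIV NAT-only donors: 0.58 × 300 = 174 HIV cases not asked, if the printed code is what gets programmed.

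**The case against.** The best defence is that Appendix 7 is not the programmed instrument. Section 4.4.1 says it supplies content and that the audio computer interview is still to be developed. The appendix carries open drafting notes and a placeholder approval number, and section 4.11 plans pilot testing. This stands as mitigation. A pilot should notice an item that no woman ever sees. It is less likely to notice a skip that lands a few items too far, and the protocol describes no routing check.

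J16a also states its population in words. That stands: the intent is clear, and total loss of J16 requires a programmer to follow the code and ignore the label.

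The job-seeking option in B14b does not prove that unemployed donors were meant to be asked, because B14b covers six months and the employment item asks about the present. That stands too. The skip is wrong because the mobility questions apply to anyone, whatever that option was for.

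Three stronger readings are tempting and are not supported:

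- *Mobility is confounded with employment and cannot be adjusted for socioeconomic status.* Asking only those not coded unemployed is a restriction and creates no confounding. Among those asked, education (B10), medical aid (B12a), self-funded private hospital care (B12b) and occupation (B13b) remain available.
- *The mobility data are missing exactly where socioeconomic status is lowest.* Not working now is not the same as lowest status. In Table 3, 49 + 90 = 139 of 300 HIV NAT-only donors (46.3%) are 25 or younger, an age range that may include students.
- *A primary hypothesis is damaged.* Mobility, dagga and vaginal practices appear neither in the Objective 1 hypotheses (section 4) nor among the named predictors in section 4.9.

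**Conclusion.** The point holds in limited form: two skip targets and one variable code are wrong as printed.

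- **Mobility** is unobserved in donors coded unemployed. Its effect in that group, or jointly with unemployment, cannot be estimated; in a complete-case model containing both, the unemployed category drops out.
- **Cannabis use** is unobserved in non-drinkers. Estimates apply to drinkers only.
- **Vaginal practices** would yield no data at all, on the condition that the printed code is programmed.

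The 174 assumes that the NAT-only sex mix of 2006 to 2010 carries over to all HIV cases. Section 4.8.1 expects about 50 NAT-only and about 160 avidity-identified infections a year, so NAT-only donors are about 50/210 = 24% of the expected pool, and the sex mix of the rest is not given. The 135 to 540 rests on an assumed 10% to 40% share. The exposures are secondary, so the main comparisons of Objective 1 are not threatened. The correction is still worth making, because answers never collected about a six-month window cannot be recovered later.

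**What to change.** Before the interview program is finalised, change three lines in Appendix 7:

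1. Route the unemployed answer to B14a instead of Section C.
2. Route the Never answer at H1 to H3a instead of H4.
3. Gate J16a on B1=2 instead of B2=2.

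If any interviews ran under the printed rules, code the skipped items as not asked, never as No, and limit inference on them to the respondents who were asked.

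The cost is three routing edits and about a minute of extra interview time for the affected respondents, against a stated 30 to 45 minutes. Section 4.6 allows up to nine months for OMB clearance of the instruments, so the cheapest moment is before that submission.
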